APPENDIX V: REPRIEVE ANCILLARY STUDY: EFFECT OF PITAVASTATIN ON KIDNEY  
FUNCTION IN HIV-INFECTED PERSONS

## BACKGROUND

With advances in HIV therapy, the incidence of HIV-associated nephropathy and subsequent end-stage renal disease (ESRD) have declined substantially [Lucas 2014; Lucas 2008; SMART 2006]. Still, 30-40% of HIV-infected persons are estimated to have Stage 1 or greater chronic kidney disease (CKD) [Gupta 2004; Overton 2012; Szczech 2004], and HIV infection remains an established risk factor for CKD, even after adjusting for traditional risk factors [Althoff 2015; Coresh 2003]. Black race, diabetes mellitus (DM) and hypertension (HTN) are common among HIV-infected persons and associated with an increased risk for CKD [Gathogo 2014; Jotwani 2012]. In fact, the effect of HIV may be additive to traditional risk factors like diabetes [Medapalli 2012].

This increased risk of CKD among HIV-infected individuals is likely mediated by inflammation [Mallipattu 2013]. HIV infection induces a paradoxical state of both immune suppression (low CD4+ T-cell count with increased risk of opportunistic pathogens) and immune activation [Deeks 2011]. The depletion of CD4+ T cells in the gut-associated lymphoid tissue facilitates excess microbial translocation and ensuing activation of both the innate and adaptive arms of the immune system [Brenchley 2006]. Such chronic immune activation translates into a well-characterized exhausted T-cell phenotype and a persistent pro-inflammatory milieu with elevated inflammatory cytokines and cellular immune activation markers, as well as markers of oxidative stress [Dolan 2005; Ross 2008]. Identifying adjunctive therapies that target these inflammatory pathways has the potential to prevent CKD in HIV-infected individuals.

In certain risk groups in the general population (DM, HTN, and pre-existing CVD), post-hoc analyses of randomized controlled trials (RCTs) have suggested that HMG-CoA reductase inhibitors (ie, statins) have a beneficial effect on the kidney. For example, in an RCT of atorvastatin for secondary prevention of strokes, eGFR improved with atorvastatin but not placebo, independent of baseline kidney function [Amarenco 2014]. These findings corroborate an analysis from the Collaborative Atorvastatin Diabetes Study, in which persons with diabetes and normal LDL-cholesterol were randomized to atorvastatin or placebo. Participants assigned to statin therapy demonstrated statistically significant improvement in eGFR that was most pronounced among persons with pre-existing microalbuminuria [Colhoun 2009]. These beneficial effects of statins have been shown to be most robust in persons with higher inflammatory biomarkers at baseline [Tonelli 2005]. These data suggest that the kidney protective effect of statins may be mediated through anti-inflammatory pathways, highly relevant in the setting of HIV infection. A recent Cochrane review of statins administered in the setting of CKD concluded that statins have uncertain effects on progressive CKD and additional prospective trials are warranted, particularly among persons with diabetes and other high-risk populations [Palmer 2014]. These post-hoc analyses from HIV negative individuals indicate that equipoise exists as to whether statins protect kidney function, particularly in populations with increased systemic inflammation, such as seen with HIV infection. Given the established association of CKD with CVD endpoints [Chronic Kidney Disease Prognosis Consortium 2010],

interventions that prevent eGFR decline and albuminuria may also have important implications for CVD and all-cause mortality.

#### OBJECTIVES

*OBJECTIVE 1: To evaluate the effects of pitavastatin on clinically relevant parameters of kidney function among HIV-infected individuals on ART.*

*OBJECTIVE 1A:* To determine whether pitavastatin is associated with a lower incidence of clinically relevant eGFR decline in HIV-infected persons.

*OBJECTIVE 1B:* To determine whether pitavastatin is associated with a lower prevalence of albuminuria.

*HYPOTHESES:* 1. We hypothesize that randomization to pitavastatin versus placebo will be associated with a lower incidence of clinically relevant eGFR decline, defined as  $\geq 30\%$  decline from baseline, a Food and Drug Administration/National Kidney Foundation (FDA/NKA) recommended surrogate endpoint for CKD [Inker 2014]. 2. We hypothesize that randomization to pitavastatin versus placebo will be associated with a lower prevalence of albuminuria, defined as urine albumin/creatinine ratio (ACR)  $> 30$  mg/g.

*OBJECTIVE 2: To assess whether the effect of pitavastatin 4 mg/daily on eGFR and albuminuria is stronger in high-risk groups defined by older age, black race, hypertension, lower CD4 cell counts, or the use of tenofovir disoproxil fumarate (TDF)-containing regimens.*

*HYPOTHESIS:* We hypothesize the kidney protective effect of pitavastatin will be stronger in high-risk groups.

*OBJECTIVE 3: To determine whether the effect of pitavastatin on kidney function is mediated through anti-inflammatory effects.*

*HYPOTHESIS:* We hypothesize that effects of pitavastatin on eGFR and albuminuria will be mediated by systemic and vascular inflammation and oxidative stress, as measured by circulating levels of key inflammatory biomarkers.

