#### SIGNIFICANCE

By adding collection of urine and blood longitudinally in at least 2500 participants, this ancillary study will definitively assess whether pitavastatin therapy will prevent significant decline in kidney function and the development of albuminuria (ACR  $> 30$  mg/g). This sample will further provide the opportunity to evaluate the effect of pitavastatin in sub-groups of HIV-infected participants for whom the risk of CKD has been demonstrated to be higher, including persons of older age, black race, hypertension, lower CD4 T-cell counts, and on tenofovir-containing regimens. Finally, the mechanisms of action will be assessed to determine whether the protective effect of pitavastatin is mediated through pathways involving inflammation and oxidative stress. Ultimately, the findings of this study will provide longitudinal data on the

epidemiology of CKD in the setting of HIV infection, provide mechanistic insights into whether statins prevent CKD by modulating inflammation and oxidative stress, and potentially change guidelines for the prevention of CKD in this at-risk population.

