#### Endpoints

For the primary analysis, we will use accepted measures of decreased eGFR. We have selected 30% decline in eGFR or ESRD for our primary outcome based on recommendations from a joint NKF-FDA workshop, which concluded that this should be considered as an alternative CKD endpoint for clinical trials [Inker 2014]. Specifically, in a pooled cohort of 850,096 individuals with eGFR  $\geq 60$  mL/min/1.73 m^2, a decline in eGFR  $\geq 30\%$  over 3 years of follow-up was associated with a hazard ratio of 7.0 for developing ESRD over the following decade. In secondary analysis, we will consider the more stringent endpoints of 40% decline in eGFR and development of eGFR  $< 60$  mL/min/1.73m^2. We will use the CKD Epidemiology

Collaboration (CKD-EPI) creatinine equation to estimate GFR, as it has been demonstrated to be more accurate than other creatinine-based formulas in both the general population and in HIV-infected cohorts [Matsushita 2010; Levey 2015; Inker 2012; Gagnieux-Brunon 2012; Bhagat 2013]. The CKD-EPI creatinine equation had statistically significantly higher accuracy and less bias than the cystatin C equation in HIV-infected persons [Inker 2012].

Albuminuria will be quantified by ACR calculated as urinary albumin in mg/dL divided by urinary creatinine in g/dL. Albuminuria is an easily assessed marker of kidney damage, which may precede eGFR decline, and is strongly linked to adverse clinical outcomes [Gerstein 2001]. Even at levels of albuminuria  $>30$  mg/g, persons are at increased risk for CVD events and all-cause mortality [Gerstein 2001; Wyatt 2010; Wyatt 2011]. We will use the ACR as a measure of albuminuria, as it is widely available in clinical practice and recommended by the IDSA Clinical Practice Guideline for CKD in HIV-Infected persons [Lucas 2014]. The ACR from a random urine sample is simple to obtain, correlates well with data from 24-hour urine collections, but is more practical and less prone to error than a 24-hour collection [Eknayan 2003].

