#### Sample Size

We will enroll a sample size of at least 2500 participants. This sample size will provide adequate statistical power to achieve our aims. We anticipate an annual event rate of 2.5% based on previous reported results [Lucas 2007; Lucas 2008]. Therefore, over 4 years, we anticipate 10% of participants will meet our primary outcome of eGFR decline. As we do not know the exact incidence of eGFR decline, we provide the minimal detectable difference based on this event rate and also for 8% and 15% incidence of eGFR decline (ie, annual event rates of 2% and 3.75%, respectively). Based on sample size of 2500 participants (50% randomized to pitavastatin and 50% placebo), a two-tailed alpha error of 5% and assuming 5% of participants will be lost during follow-up, we will have 90% statistical power to detect clinically relevant differences in the cumulative incidence of eGFR decline across randomization arms. For example, if 10% of participants randomized to placebo develop our primary endpoint over the 4-

year follow-up period, we will have 90% power to detect an absolute reduction in incidence of 3.6% associated with pitavastatin (10% in placebo vs. 6.4% in pitavastatin arm; **Table 1**). Given that albuminuria is anticipated to be a more frequent endpoint than  $\geq 30\%$  eGFR decline, we will have 90% power to detect clinically relevant differences in the percentage of participants developing this outcome measure. Previous RCTs of pitavastatin in individuals with diabetes and persons with hyperlipidemia demonstrated a 52% and 67% reduction in measures of albuminuria, respectively [Nakamura 2005; Yagi 2011]. Although we expect to see at least a 50% reduction in albuminuria in the pitavastatin group (from 15% to 7.5%) and a modest increase in prevalence of albuminuria in the placebo group [Szczech 2010], we will be powered to detect smaller differences.

Table 1. Minimal detectable difference in incidence of CKD endpoint in REPRIEVE participants randomized to pitavastatin vs placebo.

	Proportion of control population developing CKD		
Aim 1A eGFR decline	8%	10%	15%
90% statistical power	3.2%	3.6%	4.3%
80% statistical power	2.6%	3.2%	3.5%
	Proportion of control population with albuminuria		
Aim 1B % with albuminuria	15%	20%	25%
90% statistical power	4.3%	4.9%	5.4%
80% statistical power	3.8%	4.3%	4.7%

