**OBJECTIVE 2: Assess whether the effect of pitavastatin on CKD is stronger in high-risk groups defined by older age, black race, hypertension, lower CD4 cell counts, or the use of TDF-containing regimens.** We will divide the cohort based on the median age to evaluate differences between the groups above and below the median age. Similar dichotomous approaches will be taken for black race, hypertension (systolic blood pressure  $\geq 140$  mmHg, diastolic blood pressure  $\geq 90$  mmHg or antihypertensive medication use), and TDF-containing regimens. Within each sub-group studied, participant characteristics will be calculated by randomization assignment (pitavastatin or placebo). The percentage of participants developing  $\geq 30\%$  eGFR decline and separately, with ACR  $> 30$  mg/g during follow-up will be calculated for participants randomized to pitavastatin and, separately, their counterparts randomized to placebo. The statistical significance of differences within sub-groups will be calculated using interval censored regression models and chi-square tests as described in Aim 1 above. We will use multiplicative interaction terms (eg, black race \* pitavastatin) to assess differences in the effect of pitavastatin on CKD across sub-groups. We will evaluate CD4 count as a continuous variable to determine if there is a threshold below which statin therapy has greater benefit for kidney function. We will model the interaction between pitavastatin versus placebo and CD4 count as a continuous variable with interval censored regression models and logistic regression for the cumulative incidence [Howard 2011].

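### Appendix V: the albuminuria comparison mixes remission with new disease and states no use of entry ACR, so alone it cannot support the claim of preventing albuminuria

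*Protocol*

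**What the plan says.** All references are to Protocol Appendix V unless stated.

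- **Objectives.** Objective 1B is "To determine whether pitavastatin is associated with a lower prevalence of albuminuria". The hypothesis beneath it uses the same term and sets the cut-off at ACR above 30 mg/g. No visit and no restriction by entry status is given.
- **Significance.** The claim is that "this ancillary study will definitively assess whether pitavastatin therapy will prevent significant decline in kidney function and the development of albuminuria".
- **Sample Size.** The text promises 90% power for "clinically relevant differences in the percentage of participants developing this outcome measure". Table 1 instead gives the control proportion with albuminuria as 15%, 20% and 25%. The text expects at least a halving on pitavastatin, from 15% to 7.5%, and a small rise in prevalence on placebo.
- **Data Analysis Plan.** Only Aim 1A (eGFR decline) is written out. Interval-censored regression is justified there because an event is known only to fall between two visits.
- **Objective 2.** Within subgroups, the percentage with ACR above 30 "mg/g during follow-up will be calculated for participants randomized to pitavastatin" and for placebo, and is tested by the Aim 1 methods, interval-censored models included.
- **Use of entry ACR.** Protocol section 6.3.6 collects entry urine from all participants. The general analysis plans describe albuminuria at baseline, and later Objective 3 models for eGFR decline adjust for baseline ACR. No use is stated for Aim 1B or the Objective 2 albuminuria outcome.
- **eGFR <60.** The Endpoints section says: "In secondary analysis, we will consider the more stringent endpoints of 40% decline in eGFR and development of eGFR" below 60. eGFR is by CKD-EPI, while Protocol section 4.1.4 admits participants on GFR ≥60 or CrCl ≥60.

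**The concern.** Protocol eligibility has no ACR criterion, and the expected fall from 15% with a rise on placebo implies that some participants are albuminuric at entry. Follow-up prevalence then has two sources: people who entered above 30 and stayed there, and people who crossed it later. A drug that only returns existing cases to normal would lower prevalence without preventing anything. The appendix would still report that result under a heading of prevention.

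The interval-censored models in Objective 2 have a further difficulty. For a participant above 30 at entry, onset came before randomization, so there is no post-entry interval in which to place it.

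At stake is what the albuminuria result may be said to show, and whether the quoted power belongs to that statement.

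**Working it through.** **1. Reproduce Table 1 (albuminuria rows).** Inputs from Sample Size: 2500 participants, 1:1, two-sided 5%. Power = Φ{[d − 1.96·√(2p̄(1−p̄)/n)] / √[(p₁(1−p₁)+p₂(1−p₂))/n]}, solved for d.

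- At n = 1250 per arm, 90% power: 4.33, 4.93 and 5.39 points for controls of 15%, 20% and 25%. Table 1 gives 4.3, 4.9 and 5.4.
- At 80% power: 3.78, 4.29 and 4.69. Table 1 gives 3.8, 4.3 and 4.7.
- The rows match 2500 without the stated 5% loss. With it (1250 × 0.95, about 1187 per arm), power for 15% versus 10.7% is 88.0%.

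The rows are therefore correct as power for a prevalence contrast. As a relative reduction, 4.3/15 = 29%.

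**2. A difference with no prevention.** Let b be entry prevalence, s persistence and i new albuminuria among those at or below 30 at entry. Follow-up prevalence = b·s + (1−b)·i. Assume b = 15% and, on placebo, s = 70%.

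- For a placebo prevalence of 15%: i = (0.15 − 0.105)/0.85 = 5.3%.
- Keep i = 5.3% on pitavastatin, so nothing is prevented, and let persistence fall to (0.105 − 0.043)/0.15 = 41%.
- Pitavastatin prevalence = 0.062 + 0.045 = 10.7%.

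The result is 15.0% versus 10.7%, the difference that Table 1 tabulates at 90% power, from remission alone.

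**3. Size of the overlap, and power for incidence.** The documents give neither b nor s as design inputs, so both are assumed. Placebo follow-up prevalence is held at 15%, with 1187 per arm. Share already present = b·s/0.15; i = (0.15 − b·s)/(1 − b); n = 1187·(1 − b). MDD is the minimal detectable difference; the last two columns give power for a 29% and a 50% relative reduction in i.

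| b | s | Share present at entry | Placebo i | n/arm | MDD at 90% power, points (relative) | Power, 29% | Power, 50% |
|---|---|---|---|---|---|---|---|
| 5% | 50% | 17% | 13.2% | 1127 | 4.3 (32%) | 81% | about 100% |
| 5% | 70% | 23% | 12.1% | 1127 | 4.1 (34%) | 77% | about 100% |
| 5% | 90% | 30% | 11.1% | 1127 | 3.9 (35%) | 73% | about 100% |
| 10% | 50% | 33% | 11.1% | 1068 | 4.0 (36%) | 71% | about 100% |
| 10% | 70% | 47% | 8.9% | 1068 | 3.6 (40%) | 60% | 98% |
| 10% | 90% | 60% | 6.7% | 1068 | 3.1 (46%) | 48% | 94% |
| 15% | 50% | 50% | 8.8% | 1008 | 3.7 (42%) | 57% | 98% |
| 15% | 70% | 70% | 5.3% | 1008 | 2.8 (53%) | 37% | 86% |
| 15% | 90% | 90% | 1.8% | 1008 | 1.5 (83%) | 15% | 41% |

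**4. eGFR <60.** From entry value e, the fall needed to reach 60 is 1 − 60/e. This equals 30% at e = 60/0.7 = 85.7. It is 25% from 80 and 3.2% from 62, but 40% from 100. Below 85.7 the endpoint asks for less than the primary 30% decline. Someone admitted on CrCl with a CKD-EPI value already under 60 needs no fall, and no risk set is stated.

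**The case against.** The strongest reply is that nothing is wrong with the comparison. The objective and hypothesis say prevalence, Table 1 is sized on prevalence and reproduces, and randomization makes the contrast unbiased. The Background cites a statin benefit on eGFR that was most pronounced with pre-existing microalbuminuria, so including such participants is coherent. All of that stands. A reader might infer that Aim 1B is biased or invalid; the documents do not support this.

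Three other inferences also go too far:

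- *That the appendix ignores entry ACR.* It is described at baseline and adjusted for in Objective 3. The gap is confined to Aim 1B and the Objective 2 albuminuria outcome.
- *That most follow-up cases were present at entry.* This may be so, but no document gives persistence or incidence, and 17–90% does not settle it.
- *That eGFR <60 has an equal fault.* It is a secondary endpoint worded as a development, eligibility limits the overlap, and the primary 30% decline is measured from each participant's own baseline.

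One could add that interval-censored models imply an event-free start. They need one, but no text restricts the albuminuria models to such participants. It is also fair that restricting to incidence costs power. The halving that the plan expects would, however, keep 86% power or more in eight of the nine scenarios if it applied to new albuminuria.

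**Conclusion.** The concern holds as a mismatch between what is compared and what is claimed. The prevalence comparison answers Objective 1B. By itself it cannot answer whether pitavastatin can "prevent significant decline in kidney function and the development of albuminuria" as far as albuminuria is concerned, because remission alone can produce the whole tabulated difference.

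Table 1's power does not carry over to incidence. For the same 29% relative reduction, power is 88% for prevalence after the stated loss and about 15–81% for incidence. That range rests on assumed entry prevalence of 5–15%, persistence of 50–90% and placebo follow-up prevalence fixed at 15%. If 15% is the entry level and placebo rises, follow-up prevalence would be somewhat above 15% and the figures would shift.

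The eGFR <60 issue is minor: an unstated risk set, and a description as the stricter endpoint that fails for entry values below 85.7.

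**What to change.** 1. Write an Aim 1B analysis paragraph. Keep the all-participant prevalence comparison as the test of Aim 1B, at a named visit, adjusted for log entry ACR.
2. Add two separately reported outcomes: new ACR above 30 among those at or below 30 at entry, and return to 30 or below among those above it. Entry urine is collected before treatment starts (Protocol section 6.2.2), so both subsets remain randomized comparisons.
3. Limit the interval-censored albuminuria models to participants at or below 30 at entry.
4. Base any statement about prevention on the incidence analysis. Say that Table 1's power does not apply to it, and bring the Significance and Sample Size wording into line with Objective 1B.
5. For eGFR <60, restrict the risk set to entry CKD-EPI eGFR ≥60 and drop the description of it as stricter. Do not replace it with a value below 60 plus a 30% fall, which would only be a subset of the primary decline criterion.

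The cost is appendix wording and analysis code; the entry urine and creatinine are already collected. The incidence analysis has fewer participants and less power, and the two added outcomes add comparisons. Naming the prevalence test as the Aim 1B test keeps their role clear.

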#### SIGNIFICANCE

By adding collection of urine and blood longitudinally in at least 2500 participants, this ancillary study will definitively assess whether pitavastatin therapy will prevent significant decline in kidney function and the development of albuminuria (ACR  $> 30$  mg/g). This sample will further provide the opportunity to evaluate the effect of pitavastatin in sub-groups of HIV-infected participants for whom the risk of CKD has been demonstrated to be higher, including persons of older age, black race, hypertension, lower CD4 T-cell counts, and on tenofovir-containing regimens. Finally, the mechanisms of action will be assessed to determine whether the protective effect of pitavastatin is mediated through pathways involving inflammation and oxidative stress. Ultimately, the findings of this study will provide longitudinal data on the

epidemiology of CKD in the setting of HIV infection, provide mechanistic insights into whether statins prevent CKD by modulating inflammation and oxidative stress, and potentially change guidelines for the prevention of CKD in this at-risk population.

#### INTEGRATION OF OBJECTIVES INTO A5332

This ancillary study requires only modest changes to the procedures of the parent study as it will leverage the existing study infrastructure, data collection, and trial visits to allow for additional stored blood and urine collection for a longitudinal assessment of relevant kidney function parameters. As CKD and albuminuria are independent risk factors for ASCVD, this ancillary study will provide additional insight into the primary focus of the parent trial. Furthermore, only modest changes to the parent protocol and informed consent are required to facilitate these evaluations, including collection of stored blood and urine at entry and years 1, 2, and 4 of study follow up.

### STATISTICAL CONSIDERATIONS

#### Overview Considerations

Overall sample size assumptions: This ancillary study is projected to include at least 2500 persons, or approximately 38% of the total REPRIEVE study sample. The ancillary study will only recruit participants from the ACTG study sites.

General analysis plans: A baseline assessment of kidney function will be performed to assess baseline measures of kidney function and to assess clinical parameters associated with lower eGFR and albuminuria at baseline. For Objective 1, an intention-to-treat approach will be used based on randomization to pitavastatin or placebo for pitavastatin in the parent trial. For Objective 2, the effect of pitavastatin will be assessed in high-risk subgroups (HTN, age, race, tenofovir use) as outlined below. Objective 3 will utilize a case-control design to determine relevant mechanistic pathways through which the effects of pitavastatin are mediated.

General monitoring considerations: Safety of human participants participating in the kidney ancillary study will be monitored by the REPRIEVE DSMB as part of the REPRIEVE trial study monitoring plan.

OBJECTIVE 1: To evaluate the effects of pitavastatin on clinically relevant parameters of kidney function among HIV-infected individuals on ART.

